20.4.4.6 Subgroup Analyses

Subgroup analyses by clinically relevant factors will be performed and details will be provided in SAP.

### 20.4.5 Secondary Endpoint Analysis

All secondary endpoints will be summarized based on the full 12-month follow-up data of subjects in the mITT-Wave II analysis sets.

**Acute Procedural Success:** The rate of acute procedural success (defined in section 8.2.2) will be summarized descriptively.

**Freedom from Documented Symptomatic Recurrence:** The rate of freedom from documented symptomatic atrial arrhythmia (atrial fibrillation (AF), atrial tachycardia (AT) or atrial flutter (AFL)) episodes will be summarized descriptively.

**Quality of Life (QOL):** AFEQT scores assessed at baseline and follow-up visits will be summarized and compared descriptively.

### 20.4.6 Additional Endpoint Analyses

No formal statistical hypothesis and inferential statistics will be formulated and performed for the additional endpoints. Additional safety endpoints will be analyzed in Roll-in, Safety and mITT analysis sets for respectively Wave I and Wave II. Effectiveness endpoints and procedural data will be analyzed in FAS and PP analysis sets for respectively Wave I and Wave II. NAE, CT/MRA, and esophageal lesion endpoints will be analyzed in the mITT-Wave I analysis set. All endpoints will be analyzed for the roll-in analysis set separately. Details of the analyses will be described in the SAP.

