## 20.3 Analysis Sets

### 20.3.1 Wave I Analysis Sets

- **Modified Intent-To-Treat (mITT-Wave I) Analysis Set:** The mITT-Wave I analysis set will consist of enrolled Wave I subjects who meet eligibility criteria and have had insertion of the study catheter. Subjects in this analysis set who are discontinued due to:
  - study catheter related reasons will be considered acute effectiveness failures
  - non-study catheter related reasons (other equipment, pump, anatomy that precludes treatment with the study catheter or commercially available catheter) will be excluded from the effectiveness analysis.

- **Full Analysis Set (FAS- Wave I):** The FAS-Wave I Analysis Set will consist of all enrolled Wave I subjects who have had insertion of the study catheter (with or without delivery of PFA).
- **Per Protocol Analysis Set (PP-Wave I):** The PP-Wave I analysis set will consist of Wave I subjects who satisfy the following criteria:
  - are enrolled and without major protocol deviations that would affect the integrity of the data
  - have undergone ablation (PFA) with the study catheter
  - are treated for the study-related arrhythmia
  - did not require the use of a non-study catheter for Pulmonary Vein Isolation (PVI)
  - did not require ablations outside the PV region

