7.6.2 Additional Safety Endpoints

The following analyses for the additional safety endpoints will be conducted in the mITT and FAS analysis sets and summarized descriptively as the total number of events, number of subjects with events, and percentage of subjects with events:

- Occurrence of individual PAEs from the primary composite
- Occurrence of Serious Adverse Device Effects (SADEs)
- Occurrence of Serious Adverse Events (SAEs) within 7 days (early-onset), 8-30 days (peri-procedural), and >30 days (late onset) of initial ablation procedure, separately for each timeframe
- Occurrence of non-SAEs
- Occurrence of clinically symptomatic severe PV stenosis as documented by computed tomography (CT)/ magnetic resonance angiogram (MRA)

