7.6.4 Neurological Evaluations

The following analyses of neurological evaluations will be conducted using the mITT analysis set and summarized descriptively. In addition to the timepoints explicitly stated below, subjects will undergo full neurological follow-up only if neurologic symptoms and/or cerebral ischemic lesions are identified in a prior evaluation; results for these additional neurological evaluations will be summarized descriptively. Neurological evaluation questionnaires, including Mini Mental State Examination (MMSE), National Institute of Health Stroke Scale (NIHSS), and Modified Rankin Scale (mRS) will only be used in countries with validated languages. Only subjects in countries where the neurological evaluation questionnaires are applied will be included in the associated analyses.

- **Neurological Exam:** The occurrence of new or worsening neurological deficits post-ablation compared to pre-ablation will be summarized descriptively by timepoint.
- **Cerebral Emboli:** The frequency, anatomical location (side and area), and size (diameter and volume) of asymptomatic and symptomatic cerebral emboli observed pre-ablation and new emboli observed post-ablation as determined by Magnetic Resonance Imaging (MRI) evaluations assessed by a central core lab will be summarized descriptively by timepoint.
- **Mini Mental State Examination (MMSE):** The MMSE includes tests of registration, orientation (time and place), recall, attention and calculation, and language and praxis (naming, repetition, comprehension, reading, writing, and drawing)². The total score ranges from 0 to 30, with lower scores indicating greater cognitive impairment. MMSE scores pre-ablation and change from pre-ablation at the 1-month follow-up will be summarized descriptively. MMSE scores will also be plotted by timepoint.
- **National Institute of Health Stroke Scale (NIHSS):** The NIHSS is a 15-item quantitative measure of stroke-related neurologic deficit on the levels of consciousness, language, neglect, visual-field loss, extraocular movement, motor strength, ataxia, dysarthria, and sensory loss³. The total score ranges from 0 to 42, with scores equal to 0 indicating no stroke symptoms, score ranging 1-4 indicating minor stroke, ranging 5-15 a medium stroke, 16-20 a moderate to severe stroke, and a range 21-42 a severe stroke. NIHSS scores pre-ablation and post-ablation prior to discharge will be summarized descriptively and plotted by timepoint.

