7.6.5 CT/MRA

Occurrence of severe PV stenosis: Severe PV stenosis is defined as a 70% or more reduction in PV diameter compared to the PV diameter measured at baseline. The number and percentage of subjects and number and percent of targeted PVs having severe PV stenosis at 3 months post-ablation as assessed by a central core lab will be summarized in the mITT analysis set.

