7.6.6 Endoscopy

Occurrence of esophageal lesions: The number and percentage of subjects experiencing esophageal lesions as determined by post-procedure endoscopy assessed by a central core lab will be summarized in the mITT analysis set.

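### Wave I brain MRI, neurological, endoscopy and 3-month CT/MRA results are summarised in mITT only, although every other Wave I endpoint section of the SAP also reports the FAS

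*Protocol*

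**What the plan says.** Protocol 20.4.6 assigns three groups of Wave I findings to one analysis set: "NAE, CT/MRA, and esophageal lesion endpoints will be analyzed in the mITT-Wave I analysis set". Protocol 20.3.1 defines that set by two conditions: "The mITT-Wave I analysis set will consist of enrolled Wave I subjects who meet eligibility criteria and have had insertion of the study catheter". The Wave I SAP (section 5) gives the same two conditions.

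The Wave I SAP carries the assignment through:

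- 7.6.4: "The following analyses of neurological evaluations will be conducted using the mITT analysis set and summarized descriptively". This covers the neurological examination, cerebral emboli on MRI, MMSE, NIHSS and mRS.
- 7.6.5: subjects and veins "having severe PV stenosis at 3 months post-ablation as assessed by a central core lab will be summarized in the mITT analysis set".
- 7.6.6: esophageal lesions "as determined by post-procedure endoscopy assessed by a central core lab will be summarized in the mITT analysis set".

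Both documents also define a Full Analysis Set: all enrolled Wave I subjects with the study catheter inserted, eligible or not. The SAP uses it for the other safety endpoints: "The following analyses for the additional safety endpoints will be conducted in the mITT and FAS analysis sets". It also uses it as a sensitivity set for the primary safety endpoint (7.4.1).

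**The concern.** Wave I is there to characterise safety. Its scheduled brain MRI, endoscopy and 3-month CT/MRA are not repeated in Wave II, where PV imaging after the procedure is done only for symptoms. Wave II therefore cannot supply what the Wave I lesion summaries leave out.

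For safety findings, the natural population is everyone exposed to the device. Under the present wording, an ablated and imaged subject later judged ineligible contributes nothing to the core-lab summary of frequency, size and location of emboli, to the esophageal lesion rate, or to the 3-month stenosis rate by subject and by vein. Silent cerebral emboli matter most here. Protocol Table 6 says they are not primary adverse events, so the FAS run of the primary safety endpoint does not pick them up. Protocol 6.4.1 describes the risk of such emboli with pulsed field ablation as unknown. The SAP gives no reason for treating these three sections differently from the rest.

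**Working it through.** **Sets named in the Wave I SAP**

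| Section | Sets |
|---|---|
| 7.4.1 Primary safety | mITT; FAS as sensitivity |
| 7.4.2 Primary effectiveness | PP; mITT and FAS as sensitivity |
| 7.5 Secondary endpoints | PP, mITT, FAS |
| 7.6.1 Procedural data | FAS, PP |
| 7.6.2 Additional safety | mITT, FAS |
| 7.6.3 Additional effectiveness | FAS, mITT, PP |
| 7.6.4 Neurological and MRI | mITT |
| 7.6.5 CT/MRA | mITT |
| 7.6.6 Endoscopy | mITT |

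**Who is affected.** Subjects found ineligible before insertion are excluded and can be replaced (protocol 10.2, 10.3). Wave I subjects with the catheter inserted but no energy delivered do not have the extra assessments (10.3). That leaves subjects who were ablated, imaged and found ineligible after insertion.

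**What still reaches an FAS table**

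- Severe PV stenosis (a diameter reduction of 70% or more) is a primary adverse event with no symptom requirement, and it counts after day 7 (protocol Table 6 and footnote). It enters the FAS run of the primary endpoint and the FAS table of individual events. Symptomatic severe stenosis is also listed separately in 7.6.2.
- Asymptomatic cerebral emboli and esophageal injury are on the anticipated adverse event list (protocol Table 10). All adverse events must be reported (15.4.1), and 7.6.2 tabulates serious and non-serious events in the FAS. They appear there as reported events, not as core-lab rates.

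**The plan's own figure.** SAP section 6 assumes a 7% event rate and 35 subjects inserted, and states a probability above 90% of seeing at least one primary adverse event. The check is 1 − 0.93^35 = 0.921, which agrees. The choice of set for the imaging endpoints does not affect it.

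**Size of the shift.** The documents do not say how many treated subjects will prove ineligible. Take one such subject among 35, and k lesions among the 34 in mITT.

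- If that subject has a lesion, the FAS rate exceeds the mITT rate by (k+1)/35 − k/34 = (34 − k)/1190. For k = 0 this is 2.9 points; for k = 3 it is 2.6.
- If that subject has no lesion, the FAS rate is lower by k/34 − k/35 = k/1190. For k = 3 this is 0.25 points (3/34 = 8.8% against 3/35 = 8.6%).

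The bound is 1/35 = 2.9 points in either direction. At low lesion rates the larger shift is the one where a lesion is left out.

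Exact two-sided 95% intervals (Clopper-Pearson) when one lesion lies outside mITT:

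| Inserted, ineligible | mITT | FAS |
|---|---|---|
| 35, 1 | 0/34 = 0% (0 to 10.3) | 1/35 = 2.9% (0.1 to 14.9) |
| 35, 1 | 3/34 = 8.8% (1.9 to 23.7) | 4/35 = 11.4% (3.2 to 26.7) |
| 35, 2 | 2/33 = 6.1% (0.7 to 20.2) | 3/35 = 8.6% (1.8 to 23.1) |
| 40, 1 | 0/39 = 0% (0 to 9.0) | 1/40 = 2.5% (0.1 to 13.2) |

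**Chance that it matters.** Protocol 6.4.1 gives 2% to 15% for asymptomatic cerebral emboli after AF ablation. With m affected subjects, assumed independent, the chance that at least one has a lesion is 1 − (1 − r)^m. This gives 2% to 15% for m = 1, 4% to 28% for m = 2 and 6% to 39% for m = 3. The values of m are assumptions, and the range of r applies to emboli only.

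**The case against.** The case against runs as follows. The two documents agree with each other, so nothing is contradictory. Wave I tests no hypothesis. Eligibility is checked before insertion and protocol section 17 prohibits waivers, so the affected group may be empty. The intervals in the two sets overlap almost entirely. Adverse event reporting captures the events anyway, and nothing in the documents limits the Data Monitoring Committee's safety review to mITT.

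Most of this stands, and it limits the point to a missing second denominator. What it does not answer is why these summaries alone lack the FAS. In a descriptive phase, the rates and intervals are the result.

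Three stronger readings are tempting, and the documents do not support them.

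- A reader might infer that PV stenosis has no all-treated analysis. It has one, through the primary adverse event tables; only the core-lab 3-month rate lacks it.
- A reader might infer that harm is hidden. The reporting route just described argues against that.
- A reader might infer that the FAS should lead and mITT be demoted, since Wave I exclusions 31 and 32 (neurological deficit, uncontrolled reflux) concern the organs imaged. But neurological examination and MRI are required shortly before the procedure (14.2.1), so a deficit should be found before insertion. Endoscopy is scheduled only afterwards, so in a subject with uncontrolled reflux a pre-existing lesion could not be told from a device lesion. That is a reason to keep mITT in view.

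**Conclusion.** The point holds as a minor gap. For MRI and neurological results and for endoscopy, neither document provides an FAS summary. For CT/MRA, the gap is confined to the core-lab 3-month stenosis rate by subject and by vein. One affected subject shifts a rate by at most about 3 percentage points at 35 subjects, and by 2.5 at 40 (1/40). The clearest consequence is a core-lab table showing no lesions when one occurred.

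This rests on at least one ablated and imaged subject being found ineligible after insertion. The documents give no number for this, and it may be zero. It also takes 35 or 40 as the number imaged; 35 is the plan's assumption for insertion, so fewer may have the assessment. No hypothesis test depends on these summaries.

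**What to change.** In Wave I SAP 7.6.4 and 7.6.6, and in 7.6.5 for consistency, report the endpoints in the FAS among subjects who had the assessment, alongside mITT, as 7.6.2 already does. Make the same addition in protocol 20.4.6. While that section is open, replace its reference to a Safety analysis set, which 20.3 does not define; the Wave I SAP uses the FAS in its place.

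The cost is wording in two documents and a few extra descriptive tables. The set is already defined, and no new data or visits are needed. If no imaged subject proves ineligible, the two versions coincide.

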## 21. Ethics and Protection of Human Subjects

### 21.1 Ethical Standard

As the Sponsor of this study, Biosense Webster has the overall responsibility for the conduct of the study, including assurance that the study meets the regulatory requirements of the Food and Drug Administration (FDA), applicable European medical device regulation and the local government. For study under MDR, MDR2017/745 will be applicable, amending Directive 2001/83/EC, Regulation (EC) No 178/2002 and Regulation (EC) No 1223/2009 and repealing Council Directives 90/385/EEC and 93/42/EEC.

The Sponsor will also maintain compliance with GCP (ICH E6 (R2), 9 November 2016), the European standard EN ISO 14155 (Clinical Investigation of Medical Devices for Human Subjects), the Declaration of Helsinki (Ethical Principles for Medical Research Involving Human Subjects, Fortaleza 2013), Sponsor general duties (21 CFR 812.40), selection of investigators (21 CFR 812.43), monitoring (21 CFR 812.46), supplemental applications (21 CFR 812.35 [a] and [b]), maintaining records (21 CFR 812.140 [b]), and submitting reports (21 CFR 812.150 [b]), and to local regulations where required.

- **General Duties**  
Biosense Webster's general duties consist of submitting the clinical investigation application to appropriate regulatory agencies, assuring that sites have received EC

approvals prior to shipping the devices, selecting investigators, ensuring proper clinical site monitoring and ensuring subject informed consent is obtained.

- **Data Quality and Reporting**  
Biosense Webster is responsible for providing quality data that satisfy federal regulations and informing proper authorities of serious unanticipated AEs and deviations from the protocol.
- **Selection of Investigators**  
All potential investigational sites will undergo an evaluation to ensure that the site has the appropriate facilities and personnel to conduct the study in compliance with the clinical investigational plan. Based on outcome of evaluation process, Biosense Webster will select qualified investigators, ship devices only to participating investigators, obtain a signed Investigator's Agreement and provide the investigators with the information necessary to conduct the study.
- **Supplemental Applications**  
As appropriate, Biosense Webster will submit changes in the Clinical Investigational Plan to the investigators to obtain all applicable re-approvals.
- **Maintaining Records**  
Biosense Webster will maintain copies of correspondence, data, adverse device effects and other records related to the study. Biosense Webster will maintain records related to the signed Investigator Agreements.
- **Submitting Reports**  
Biosense Webster will submit any required regulatory reports identified in this section of the regulation. This may include UADEs, withdrawal of EC approval, current investigators list, annual progress reports, recall information, final reports and protocol deviations.

## **21.2 Informed Consent Process**

### **21.2.1 Informed Consent Procedure and Documentation**

Subjects informed consent must be obtained and documented according to the principles of informed consent in the latest version of the Declaration of Helsinki (Fortaleza, 2013), ISO 14155, and approved by the reviewing CA and EC.

Informed consent is mandatory and must be obtained from all subjects prior to their participation in the study.

Prior to screening or performing any study related procedures that are solely for the purpose of determining eligibility for this study, any potential benefits and risks of the study must be explained to the subject. Subjects will be informed about aspects of the study that are relevant to the subject's decision to participate. Subjects should be made aware that by signing the ICF, they are granting approval for study personnel to review their medical records and to collect/analyze personal medical information. Subjects should also be informed that study personnel will maintain confidentiality of the medical records at all times.

The ICF will be written in a native, non-technical, language that is understandable to the subject and is to be approved by the applicable EC prior to enrolling subjects. The subject or designee will be provided with ample time to read and understand the ICF and to consider participation in the study. Informed consent will be requested prior to enrollment and must be personally signed and dated by the subject, or subject's legal representative, prior to performance of any study related activity or procedure. If a subject is unable to read or write, informed consent shall be obtained through the aid of an independent witness who will be present throughout the process. The written ICF and any other information shall be read aloud and explained to the prospective subject and, whenever possible, subject shall sign and date the ICF. The witness must also sign and date the ICF attesting that the information was accurately explained, and that informed consent was freely given. The point of enrollment corresponds with the time that subjects signs the informed consent.

The investigator and/or designee must also clearly document the process of obtaining informed consent in the subject's source documents. The voluntary process of obtaining informed consent confirms the subject's willingness to participate in the study. It's the investigator's responsibility to ensure that the informed consent process is performed in accordance with ICH-GCP and, where applicable, local and federal regulations. Subjects should not be coerced, persuaded, or unduly influenced to participate or continue to participate in the trial. Subjects or his/her legal representative must be given ample time and opportunity to inquire about details of the trial and all questions about the trial should be answered to the satisfaction of the patient or the representative. Failure to provide written informed consent renders the subject ineligible for the study. If new information becomes available that can significantly affect a subject's future health and/or medical care, this information shall be provided to the subject(s) affected in written form. If relevant, all affected subjects shall be asked to confirm their continuing informed consent in writing by dating and signing the amended ICF.

### **21.3 Participant and Data Confidentiality**

During this clinical investigation, all representatives of the Sponsor will comply with all in-country privacy laws and regulations regarding contact with subjects, their medical record information, copying of information, and protection of the subject identities.

All information and data sent to Biosense Webster concerning subjects or their participation in this clinical investigation will be considered confidential. Only authorized Biosense Webster personnel or representatives (including contracted service providers, i.e. Core Lab, Clinical Research Associate, CRO, etc.), representatives of the FDA or CAs acting in their official capacities will have access to these confidential files upon request (including, but not limited to, laboratory test result reports, ECG reports, admissions/discharge summaries for hospital admission occurring during a patient's study participation and autopsy reports for deaths occurring during the clinical investigation). Some of the countries to which the study subjects and investigators personal data may be transferred may not offer as comprehensive a level of protection of personal data as within the European Union but Sponsor will take all reasonable steps to ensure a sufficient level of data protection. All data used in the analysis and reporting of this evaluation will exclude identifiable reference to the subject.

### 21.3.1 Research Use of Stored Data

- Intended Use: Data collected under this protocol may be used to study AF.
- Storage: Access to stored data will be limited. Data will be stored using codes assigned by the sponsor. Data will be kept in password-protected computers. Only investigators and the sponsor will have access to the data.

## 22. Source Documents and Access to Source Data/Documents

Data entered on to the eCRFs will be taken from source documentation, such as hospital procedure reports, admission and discharge summaries, other hospital or investigator office/clinic documents, and system data (CARTO, generator system). If unique study parameters are not documented on standard hospital or office reports, a worksheet may be developed to record this information. The worksheet shall be signed by the PI or authorized designee and will serve as source document and as basis for monitoring the eCRFs. Electronic subject records will be considered as source documents on the condition that the hospital's database is a validated system. If this is not the case, electronic records should be printed and added to the subject's paper file. A print-out of a completed eCRF cannot be used as source documentation.

Investigators should maintain information in the subject's medical records, which corroborate data collected on the eCRFs. In order to comply with these regulatory requirements, at minimum, the following is a list of information that should be maintained.

- Medical history/physical condition of the study subject before involvement in the study sufficient to verify protocol selection criteria (if not already present).
- Dated and signed notes from the day of entry into the study including the study Sponsor (Biosense Webster), protocol number, clinical site, subject number assigned and a statement that consent to participate in the study was obtained.
- Dated and signed notes from each study visit with reference to the eCRFs for further information, if appropriate (for specific results of procedures and exams).
- Reports on AEs and their resolution, including supporting documents such as discharge summaries, EP lab reports, ECGs, lab results.
- Notes regarding protocol-required medication and prescription medications taken during the study (including start and stop dates).
- Notes on subject's condition upon completion of or withdrawal from the study.

Only authorized Biosense Webster personnel or representatives, authorized site personnel, local government authorities, or the FDA, acting in their official capacities, will have access to these confidential files.

